### 8.1.2 Methodology for analysing the main objective

Any AF re-occurrence event (Tables 5, 6 and 7) during the “blanking period” will be not be considered. “Blanking period” starts with the day of the first documented procedure and ends at exact 90 days. The first documented date of AF re-occurrence will be set as the event date. “Blanking period” for patients with additional procedure(s) at any time will not be started newly, they will be considered as “not-event free” at time of the first additional procedure.

Freedom from AF re-occurrence at 12 months will be estimated using Kaplan-Meier methods (time-to-first-event-analysis). A point estimate at the date of 12MFU post first documented procedure will be presented. Standard error will be approximated using

Greenwood's formula, and a two-sided 95% log-log confidence interval will be presented. For patients without a reported AF re-occurrence event, those patients will be censored. In this case, the right-censoring time will be set to the last study contact date. Main objective Kaplan-Meier estimation results will be displayed in percentages at 12 months (351 days) after first documented procedure. Estimated AF re-occurrence rates by month (at the end of month 3 to 11 after first documented-procedure) will be calculated and displayed as well. For group comparisons Log-Rank test will be applied. Also, Hazard ratios and 95% confidence intervals will be shown (for group comparisons, please see SAP chapter 8.6). For Kaplan-Meier estimation, numbers at risk will be displayed for reasonable points in time.

Re-occurrence of AF during 12 months (considering the "blanking period") will also be analysed via Cox proportional hazard regression model presenting hazard ratios and the corresponding 95% CI. Independent variables will be determined by Phased RFA procedure experts or physicians. Cox modelling for AF re-occurrence will be done for all pre-defined subgroups (FAS patients) where the analysis scope is the 12 month outcome (SAP chapter 8.6.1). Further Cox modelling (e.g. for multiple AF events) may be applied.

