7.2.1 Frequency of Follow up

Data collection will be completed following standard of practice procedures at each participating site. Most of the sites have a standard of care for post AF ablation visits to invite patients for the medical checkup after the "blanking period" which is lasts around 3 month after the ablation procedure; some sites also see patients at 6 and 12 months after the Phased RFA.

To mitigate variations in clinical care practices for analysis, the visit windows below are proposed to aligning with typical care practices for this therapy. Data analyses will include follow up visits, regardless of when they occur.

Table 7-2: Follow Up Visit Windows

| Months | Window Starts (days post procedure) | Target (days post-procedure) | Window end (days post-procedure) |
|-----------|-------------------------------------|------------------------------|----------------------------------|
| 3 months | 85 | 90 | 100 |
| 6 months | 175 | 180 | 190 |
| 12 months | 351 | 365 | 425 |

Additional data collection activities may be completed using sub-studies under the GOLD AF Registry protocol. Sub-studies may be developed to satisfy local data needs and/or evaluate additional areas of scientific interest. Sub-studies must be reviewed and approved by Medtronic and will be documented and managed under separate cover.

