## 8.1 Statistical analyses for the main objective

### 8.1.1 Estimate Phased RFA 12 month success rate

Success rate estimated as the time to first AF re-occurrence event from the first documented procedure. Data about AF events will be collected since the first documented procedure, including 90 days of the "blanking period" and closes at 12 months FU. If no AF events occur during the follow-up period (considering the "blanking period") up to 12 (+2) months, the case is considered to be "event-free". Calculations will be done for exact 12 months (351 days) after first documented procedure.

Main objective will be calculated for the BAS, FAS and EFAS (see chapter 4 and Appendix B). A successful first documented procedure (successfulness by PVI confirmation) is the basis to calculate the main objective. Patients with a procedure during the "blanking

---

 in the service agreement #2 refers to the final report, which is one and the same document for this study

period" of 90 days after first documented procedure will be excluded from main objective calculations.

Predefined AF re-occurrence definition from CIP Version 2.0 will not be applied to calculate the main objective. Further analysis might be used to estimate Phased RFA success rate considering (re-)occurring left Afl events.

AF re-occurrence event defined as:

- AF pharmacological and/or electrical CV
- AF more the 30 sec on ECG/EGM
- AF less than 30 sec in combination with AF symptoms
- Re-ablations for AF

For this analysis adjudicated AE data and coded AE data (free text fields) will be used. AF re-occurrence event rate will be estimated with and without the use of antiarrhythmic drugs at time of the 12 month follow-up. AF re-occurrence rates will be calculated for patients from BAS and FAS (Appendix B) which need to have a signed 12 month FU / 12 month FU by phone form by definition. AF re-occurrence is defined as the first event of AF re-occurrence event and their related date information based on the following eCRF forms and data fields:

**Table 4:** Main objective variables at 12MFU / General FU form

eCRF field	Related date field	Related FID's annotated eCRF (V1.3, V1.4)
Reason for visit: AF re-occurrence	Date of visit	F11000050 F11000010
Re-ablation reason: Due to AF- occurrence	Date of visit	F11000070 F11000010
History of arrhythmias since last visit: AF	Date of first occur- rence	F12000012 F12000050

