History of arrhythmias since last visit: Re- ablation for AF	Date of re-ablation for AF	F12000060 F12000070
CVD hospitalizations during last visit: AF	Date of first admis- sion	F15000020 F15000030

**Table 5:** Main objective variables at 12MFU by phone form

eCRF Field	Related date field	Related FID's annotated eCRF (V1.3, V1.4)
History of arrhythmias since last visit: AF	Date of first occur- rence	F13000010 F12000050
History of arrhythmias since last visit: Re-ablation for AF	Date of re-ablation for AF	F12000060 F12000220
CVD hospitalizations during last visit: AF	Date of first admis- sion	F15000010 F15000020_1 F15000030

**Table 6:** Main objective variables at AE form

eCRF Field	Related date field	Related FID's annotated eCRF (V1.3, V1.4)
Other diagnostics: ~ "AF"	Date of AE	F31000010_88 F30000090 F30000010

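### The blanking rule omits SAP Table 4, and AF dated only by the visit has no rule for a conflict with the AF dates on the same form

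*SAP*

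**What the plan says.** SAP 8.1.1 builds the main endpoint from three tables: Table 4 (General FU and in-hospital 12-month form), Table 5 (12-month phone form) and Table 6 (AE form). Table 4 has five rows.

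- Two rows take the date of visit (F11000010): "Reason for visit: AF re-occurrence" and "Re-ablation reason: Due to AF- occurrence".
- Three rows carry their own date: "History of arrhythmias since last visit: AF" (date of first occurrence, F12000050), "History of arrhythmias since last visit: Re- ablation for AF" (date of re-ablation, F12000070) and AF hospitalisation (date of first admission, F15000030).

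SAP 8.1.2 then gives the date rules. The blanking sentence begins "Any AF re-occurrence event (Tables 5, 6 and 7) during the" and removes events in the blanking period, which "starts with the day of the first documented procedure and ends at exact 90 days". The next rule reads: "The first documented date of AF re-occurrence will be set as the event date". The Kaplan-Meier estimate is read at day 351.

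The 12-month visit lies at or after that day. Protocol Table 7-2 gives a window from day 351 to 425 with target day 365, and SAP 7.2.3 uses later than day 351. Protocol 7.2.1 says most sites see patients for a check-up after the blanking period, "which is lasts around 3 month after the ablation procedure".

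**The concern.** The blanking sentence is the one a programmer will implement for the main endpoint, and its table list is wrong. Table 4, which holds every General FU and in-hospital 12-month event, is missing. Table 7, which lists procedure-safety variables, is included.

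The visit-reason row raises a separate problem. When it and the AF history row on the same form carry different dates, the SAP does not say which governs. It also does not say whether blanking is applied to each record before the first date is chosen, or afterwards. Whether a patient fails, and when, can then depend on the date of attendance rather than the date of AF. Early AF can be counted as a recurrence, and AF before day 351 can be moved past the read-out. Table 5 has no visit-dated row, so the dating also depends on whether the 12-month contact was in hospital or by phone, although both feed one estimate.

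**Working it through.** **Table reference.** SAP 8.1.1 applies the blanking period to AF events in general, with no restriction by table. SAP 8.1.2 restricts it to Tables 5, 6 and 7. Followed to the letter, AF on day 60 entered as history on a General FU form (Table 4) is an event at day 60. Under 8.1.1 it is not. The two sections cannot both be implemented.

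**Tracing the date rules.** Blanking is now taken to apply to Table 4 as well. Order A drops records dated day 90 or earlier and then takes the first remaining date. This follows the order of the sentences in 8.1.2. Order B takes the first date and then blanks it.

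| Case | Event date, A | Event date, B | Result at day 351 |
|---|---|---|---|
| 1. AF day 60; only entry is visit reason, visit day 95 | 95 | 95 | counted as recurrence |
| 2. AF day 60 entered as first occurrence; visit reason AF, day 95 | 95 | none | depends on order |
| 3. AF day 60 found at routine check-up day 95, entered only as history | none | none | correctly blanked |
| 4. AF day 250; only entry is visit reason at 12-month visit, day 380 | 380 | 380 | missed |
| 5. As 4, with first occurrence day 250 also entered | 250 | 250 | correctly counted |
| 6. AF day 250 reported on the phone form | 250 | 250 | correctly counted |
| 7. Visit reason only, 12-month visit exactly on day 351 | 351 | 351 | counted |

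Order B is not a remedy. A patient with AF on day 40 and a true recurrence on day 150 has first date 40, which is blanked, and the recurrence is lost.

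**Re-ablation row.** SAP 8.1.1 excludes patients with a procedure in the blanking period. SAP 8.1.2 counts a later additional procedure at its own time, and re-ablation has its own date field. The visit-dated row therefore matters in two situations only: the re-ablation date is missing, or a redo with another technology is not treated as a procedure. For such redos, Protocol 7.2 requires no Procedure CRF, only the General FU entry.

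**Benchmark for size.** The plan (SAP 3.3) states ±3.8% for n = 800, prevalence 20%, design effect 1.2.

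- Recomputed: 1.96 × √(1.2 × 0.2 × 0.8 / 800) = 3.04%. The stated figure does not reproduce at 20%. It matches a prevalence of 50%: 1.96 × √(1.2 × 0.5 × 0.5 / 800) = 3.80%.
- With no censoring before day 351, each patient whose day-351 status is wrong moves the estimate by 1/800. So 0.038 × 800 = 30.4 patients, or 0.0304 × 800 = 24.3, shift it by one half-width.

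**Illustration, on assumed values.** Let e = 0.26 be true events between days 91 and 351. This gives 74% success, the average figure in Protocol 4.4.1 for the earlier platinum catheter, used here only as a reference. Let f be the share of these events dated only by a 12-month visit after day 351. Let b be the share of patients given a false event just after day 90, taken as independent of later events. Then S(351) = (1 − b) × (1 − e(1 − f)).

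- b = 0: f = 10%, 25%, 50% gives 76.6%, 80.5%, 87.0%.
- f = 0: b = 1.5%, 3%, 6% gives 72.9%, 71.8%, 69.6%.
- b = 3% with f = 10%: 0.97 × 0.766 = 74.3%. The two errors nearly cancel, so a plausible overall rate would not show that either is absent.

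**The case against.** The strongest reply is that the rules mostly work. AF history since the last visit is collected on every follow-up form and has its own date. Protocol 7.4 marks all fields as required by default, and queries are raised for incomplete data. Where the onset date is entered, AF at day 250 is counted at day 250. The table list is probably a numbering slip, since 8.1.1 states the intention. Table 13 also plans curves with and without blanking and out to 14 months.

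Much of this stands, and it rules out several stronger readings.

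- A reader might infer that the usual post-blanking check-up turns early AF into failures. It does not. SAP 3.1 separates visits due to the site's schedule from visits related to AF re-occurrence, and a check-up not recorded as made for AF is unaffected (case 3). If AF is documented at a visit after day 90, the visit date is a valid recurrence date.
- A reader might infer that AF reported at the 12-month visit is generally lost. That happens only when no dated companion field is filled.
- A reader might infer that General FU events are deliberately left unblanked. SAP 8.1.1 says otherwise.

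Some of the reply does not stand. Protocol 7.4 allows navigation with fields missing, and SAP 7.5.1 does not replace missing values, so visit-only dates are possible. The annotated eCRF is not in the text available here, so whether an onset date is mandatory cannot be checked. Complete data also does not settle case 2, where both dates are present and conflict. The Table 13 curves show part of the effect but do not correct the main estimate.

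**Conclusion.** The point holds in a limited form. The table reference is wrong on its face and contradicts SAP 8.1.1; this needs no assumption. The visit-reason row can count AF confined to days 0 to 90 as a recurrence, but only if the patient attends after day 90 with AF re-occurrence recorded as the reason. It can miss AF before day 351, but only if a 12-month visit after that day is the sole date. The phone form is unaffected, and the re-ablation row matters only in the two situations above.

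Neither the size nor the net direction can be derived from the documents. A reader might multiply an assumed 10–20% of patients with early-only AF by an assumed 25–50% seen later for that reason, and obtain 2.5–10% false failures. Neither input is in the documents, and the opposing error is left out. The defensible statement is the benchmark: about 24 to 30 patients in 800, misdated in one direction and with no earlier censoring, shift the estimate by 3.0 to 3.8 points. That is enough to settle the rules before the final analysis.

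**What to change.** In SAP 8.1.2:

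1. Correct the blanking reference to Tables 4, 5 and 6.
2. Judge blanking on the date AF occurred. Let a visit-reason row create an event at the visit date only if AF is documented at that visit or the form records AF after day 90. If all AF on the form is dated on or before day 90, the row creates no event.
3. Where an onset, re-ablation or admission date after day 90 exists, use the earliest such date instead of the visit date.
4. Where the visit date is the only date, state the main handling in advance, list the cases, and run a sensitivity analysis, for example with the event placed between the previous visit and this one.

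The SAP should also say whether a redo with another technology counts as a procedure.

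Do not simply re-date the visit-reason row by F12000050. That field holds only the first occurrence. A patient with AF on day 40 and again on day 95, seen on day 95 for AF, would be re-dated to day 40 and blanked, and a true recurrence would disappear.

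The cost is SAP wording, a small change in the event derivation and one listing with a sensitivity run. The date fields named here are already in Table 4.

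### A follow-up form that spans day 90 and carries only an early first-AF date can hide later AF, which biases 12-month success upward; SAP 8.1.2 has no rule for this case

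*SAP*

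**What the plan says.** **Event sources.** SAP 8.1.1 bases recurrence on the fields in Tables 4 to 6. On the visit forms and the phone form, the item "History of arrhythmias since last visit: AF" is paired with "Date of first occur- rence". The item "CVD hospitalizations during last visit: AF" is paired with the date of the first admission. Other dated sources are a visit with "Reason for visit: AF re-occurrence" (Table 4 only), re-ablation for AF, and AF coded from the AE form. SAP 8.1.2 also makes the first additional procedure an event.

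**Blanking.** SAP 8.1.2 states: "Any AF re-occurrence event (Tables 5, 6 and 7) during the “blanking period” will be not be considered". The period starts on the procedure day and "ends at exact 90 days". The next rule is "The first documented date of AF re-occurrence will be set as the event date". A patient with no counted event is censored at last contact.

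**Timing of contacts.** The Protocol synopsis and SAP 3.1 describe all follow-up visits as unscheduled, and the 12-month contact may be by phone. Protocol 7.2.1 reports that most sites hold a check-up at about 3 months and that "some sites also see patients at 6 and 12 months after the Phased RFA".

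**Related analysis.** SAP 8.8, Table 13, plans Kaplan-Meier curves with and without the blanking period.

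**The concern.** A field that records only the first AF date in an interval suits a time-to-first-event analysis that starts at day 0. It does not suit one that starts at day 90. When the interval crosses day 90 and the first date falls before it, the form says nothing about AF after day 90, yet the analysis treats the patient as having had none. AF hospitalisation, dated by first admission, has the same weakness.

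The registry's main estimate is at stake. The error in the 12-month success rate runs one way, towards success. It grows as contacts become sparser, so it would also distort any comparison of success between sites or countries with different visit habits. After lock, the listed fields cannot separate a patient with AF only in the blanking period from one with AF before and after it.

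**Working it through.** The plan gives no figure to reproduce here, so the check applies the derivation rule to example patients.

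**Rule applied.** Each form contributes the earliest AF date, and the earliest AF admission date, since the previous contact. Dates of AF-triggered visits and re-ablations are added. Dates up to day 90 are dropped. The earliest remaining date is the event. In every row the last contact is a 12-month form on day 395.

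| AF on days | Earlier contacts | Dates obtained | Result |
|---|---|---|---|
| 40 | none | 40 | event-free (correct) |
| 40, 200 | none | 40 | event-free (wrong) |
| 40, 150 | routine visit day 180 | 40 | event-free (wrong) |
| 40, 200, both admissions | none | 40, 40 | event-free (wrong) |
| 40, 150, 300 | routine visit day 180 | 40, 300 | event day 300, not 150 |
| 40, 200 | visit day 95 | 40, 200 | event day 200 (correct) |
| 40, 200 | visit day 200 because of AF | 40, 200 | event day 200 (correct) |
| 40, 200 | re-ablation day 200 | 40, 200 | event day 200 (correct) |

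The first two rows leave identical AF dates. The fifth row shows late dating, which affects the monthly rates planned in SAP 8.1.2. A visit soon after day 90 does not give full protection: if AF began on day 60 and is still present at a routine day-95 visit, that form carries day 60 and is blanked.

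**Do the other listed fields fill the gap?**
- ECG/EGM findings and cardioversion define events in SAP 8.1.1, but Tables 4 to 6 list no dated field for either. Protocol 3.4 says the General FU form collects both. Whether they carry dates depends on the annotated eCRF (SAP Appendix E), which is not reproduced.
- The AE form is a narrow route, because Protocol section 11 collects only procedure-related and system-related events.
- Table 5, for the phone form, has no reason-for-visit field.

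**Size.** Overstatement of 12-month freedom ≈ E × L × U, where E is the proportion with AF in blanking, L the proportion of these with later AF, and U the proportion of those whose later AF no listed date captures. The documents give none of the three. Under assumed ranges:
- low: 0.20 × 0.30 × 0.10 = 0.006, or 0.6 points
- middle: 0.35 × 0.50 × 0.25 = 0.044, or 4.4 points
- high: 0.50 × 0.70 × 0.50 = 0.175, or 17.5 points

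The spread shows how little is known. U should be small where a 3-month visit is routine.

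**Bounds for unresolved forms.** Let m of N patients be unresolved and let S be 12-month freedom in the others. Ignoring other censoring before 12 months:
- event at day 91: S(N − m)/N
- censored at day 90: S
- event-free to last contact (the current rule): [S(N − m) + m]/N

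The outer two differ by m/N, so each 1% of patients left unresolved widens the range by 1 point. Censoring at day 90 lies between them and is not the favourable extreme.

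**The case against.** The strongest case on the other side has five parts.

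- **Other dates count.** A reader might infer that the rule uses only the first AF date, so that early AF always hides later AF. The documents do not support that. AF-triggered visits, re-ablations, AE dates and additional procedures all supply dates, and each new form opens a new interval. This stands and narrows the point.
- **The usual visit pattern helps.** Protocol 7.2.1 says most sites see patients at about 3 months, which closes the early interval. This stands: masking is not the usual pathway. It does not help patients without such a visit, and no visit near day 90 is required.
- **The event-date sentence may be sound.** Read after the blanking sentence, it can mean the first date that remains. That is a fair reading. The loss comes from the single-date fields and the missing rule for spanning forms, not from that sentence alone.
- **The curve without blanking brackets the problem.** It counts every patient with a recorded early date as a failure. It also counts patients whose AF was confined to blanking, and it dates all of them early, so the bracket is loose and resolves nobody.
- **The registry is descriptive and the size is unknown.** Both are true, and both lower the severity. A descriptive estimate can still be biased.

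**Conclusion.** The plan is wrong as written on this point, with moderate severity. Following SAP 8.1.1 and 8.1.2 literally counts some patients with AF after day 90 as event-free and dates others late. The direction is certain: 12-month success can only be overstated by this route. The affected group is limited to patients with a form spanning day 90, a first-AF or first-admission date on or before day 90, and later AF in that interval that no other listed date captures. It is largest where the 12-month phone form, or a visit at 6 months or later, is the first contact.

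The size cannot be derived from the documents. The 0.6 to 17.5 points above rest wholly on assumed probabilities. A reader might set such figures against the ±3.8% precision in the sample-size sections and conclude that the bias matches or exceeds it. That comparison is not supported: ±3.8% is stated for a 20% prevalence of re-ablation, not for freedom from AF. A count of affected forms would replace the assumptions.

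**What to change.** 1. In SAP 8.1.2, state that the event date is the first qualifying date after day 90. Correct the table reference to Tables 4, 5 and 6: Table 7 is the procedure-safety table, and Table 4, which holds the General FU and in-hospital 12-month fields, is not cited.
2. Before final lock, list every form whose interval spans day 90 and whose first-AF or first-admission date is on or before day 90. Report the number. Query the site for the first AF date after day 90, and use any dated evidence after day 90 already on the form (cardioversion, ECG/EGM) where it exists.
3. For forms that stay unresolved, report the 12-month estimate with these patients as events at day 91 (least favourable) and as event-free to last contact (the current rule, most favourable), with censoring at day 90 as an intermediate case.

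The cost is a few lines of SAP text, a short query list and one sensitivity table. The success rate may come out less favourable.
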